	
The above dosages may be adjusted based on the results of PK Run-in Part.
 
Part B (2 to < 12 years, ≥ 10.0 kg):
 
 
• KAF156 and LUM-SDF (up to 3 cohorts selected depending on the outcome of Part A)
 
• Coartem® BID for 3 days
 

Efficacy assessments	
 
• Parasitaemia
 
• Blood sample for molecular diagnostic purposes
 

PK assessments	
 
• PK parameters of study drugs (measured by AUC0-24h, AUClast, AUCinf, Cmax, Tmax, T1/2)
 

Key safety assessments	
 
• Physical examination and malaria signs and symptoms
 
• Vital signs
 
• Body temperature
 
• Monitoring of laboratory parameters in blood and urine
 
• Electrocardiogram
 
• Adverse event (AE) monitoring
 

Other assessments	
 
• Additional back-up blood samples for certain specific safety biomarkers (e.g., miR122) will be collected and analyzed if required
 

Data analysis	
For the PK Run-in Part, the primary objective is to investigate the pharmacokinetic interaction potential between KAF156 and lumefantrine-SDF. 2-sided 90% confidence intervals for PK parameters of KAF156 and lumefantrine will be calculated.
 
Subsequent statistical analyses for Part A and Part B will be performed separately and similarly. For ACPRs (PCR corrected and uncorrected ACPR at Days 15, 29, and 43), 2-sided 95% confidence intervals for each treatment group will be constructed using the exact (Pearson-Clopper) method. For parasite clearance time and fever clearance time, descriptive statistics (mean, standard error, median, quartiles) for each treatment group will be presented using the Kaplan-Meier method.

Key words	Plasmodium falciparum malaria, KAF156, LUM-SDF, adults, children

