#### **9.5.1.3 Parasite clearance time (PCT) and fever clearance time (FCT)**

Descriptive statistics (mean, standard error, median, quartiles) will be presented using the Kaplan-Meier method. Kaplan-Meier curves will be provided.

PCT will be calculated based on uncorrected parasite counts. Patients without parasite clearance for whatever reason will be censored at the time of last parasite assessment. Patients who were enrolled on the basis of history of fever and did not subsequently have a fever at pre-dose will not be included in the analysis of FCT. Patients without fever clearance for whatever reason will be censored at the time of last temperature assessment.

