2.1.1 General definitions

Study treatment: KAF156, Lumefantrine solid dispersion formulation (LUM-SDF), and Coartem[®]. KAF156 and LUM-SDF are part of investigation treatments whereas Coartem[®] will be served as control. They are referred to as study treatments in the document.

Treatment group name, instead of cohort number, will be used in statistical analyses and outputs. The following abbreviated treatment groups will be used as the headers in the CSR outputs:

- KAF200 mg/LUM960 mg-1D (for PK run-in part) or KAF200 mg/LUM960 mg-1D in case the description is too long
- KAF400 mg/LUM960 mg-1D
- KAF800 mg/LUM960 mg-1D
- KAF400 mg/LUM960 mg-2D
- KAF200 mg/LUM480 mg-3D
- KAF400 mg/LUM480 mg-3D
- KAF400 mg/LUM960 mg-3D
- Coartem

Baseline: The last measurement made prior to administration of the first dose of study treatment. Note this may include measurements taken on the day of randomization (e.g. lab, ECG, vitals). If a patient did not receive any dose of study treatment then the date at randomization date will be used as the date of first dose of study treatment.

Study day: Study day will be calculated with respect to the first dose of study treatment. The first day of administration of study treatment (first dose) is defined as Day 1. Day -1 will be the day before Day 1. Day 0 does not exist. Due to the multiple assessments collected more than once for a day in the treatment phase for some variables, the study day calculation is based on the treatment start date and time.

For the assessments that are performed more than once for a day:

On or after Day 1 up to Day 3, study day = Integer (datetime of assessment – datetime of first dose of study treatment)/(60*60*24) + 1.

For assessments collected after Day 3, study day = date of assessment – date of first dose of study treatment + 1.

For assessments that are performed once for a day: study day = date of assessment – date of first dose of study treatment + 1.

For assessments collected prior to Day 1, study day = date of assessment - date of first dose of study treatment.

Tail of KM plots: Since the tail of KM plots after the day of last planned assessment is not reliable due to small numbers of patients at risk, the time to event will be reset to planned last day regardless of censoring.

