2.5.4.1 Analysis of PCR-corrected ACPR rate using Kaplan-Meier method

For the FAS, the proportion of patients with PCR-corrected ACPR at Day 29 and 95% CI will be also estimated using the Kaplan-Meier method ([Stepniewska and White 2006](#) and [WHO 2015](#))

Event = PCR-corrected non-responder during the study (same as at Day 15, Day 43, See Section 2.1). The event time is the first time when the patient becomes a non-responder based on PCR-correction. If a patient parasite is not cleared at all, Day 7 is considered as the event time.

The PCR-corrected responder rate at Day 29 is estimated by the survivor function at Day 29 using the Kaplan-Meier method.

Rule for censoring:

The following censoring rules will be applied to the patients who were not non-responder

- Patients who had a new infection (i.e., reinfection) with *P. falciparum* or other species without *P. falciparum* recrudescence on or after Day 8 will be censored at the first time of the PCR that indicate the infection or blood smear with other species;
- Patients who received non-rescue antimalaria medication for other infections, such as *P. falciparum* gametocytes, will be censored at the first time of antimalaria medication;
- Patients who have parasites at Day 8 or later but cannot be determined as recrudescence or new infection due to missing PCR genotyping will be censored at the time of the first malaria blood film with presence of parasites on or after Day 8.
- other patients not classified as non-responder will be censored at the time of last parasitemia assessment.

A two-sided 95% CI for the difference in proportion of responders between each KAF156/LUM-SDF combination treatment group and Coartem[®] will be calculated based on the variance of individual proportion using the Greenwood formula.

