2.7.2.3 Parasite clearance time (PCT) and fever clearance time (FCT)

Descriptive statistics (mean, standard error, median, quartiles) will be presented using the Kaplan-Meier method. Kaplan-Meier curves will be provided.

PCT will be calculated based on uncorrected asexual parasite counts. Patients without parasite clearance for whatever reason will be censored at the time of last parasite assessment. Patients who were enrolled on the basis of history of fever and did not subsequently have a fever at pre-dose will not be included in the analysis of FCT. Patients without fever clearance for whatever reason will be censored at the time of last temperature assessment. Patients who received any antimalarial medication (including rescue medication) before (parasite or fever) clearance will be censored at the first use of antimalarial medication. The difference between each test group and control will be evaluated using a log-rank test. Patients who did not experience a clearance will be censored at the time of last relevant assessment (parasite or fever). For the pooled analysis, the log-rank test will be stratified by Part.

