5.6.3 Other secondary XXXXXXXXXX analysis

Kaplan-Meier estimates

An estimate of the survival function in each treatment group will be constructed using Kaplan-Meier (product-limit) method as implemented in PROC LIFETEST with METHOD=KM option. The PROC LIFETEST statement will use the option CONFTYPE=LOGLOG.

Median survival for each treatment group will be obtained along with 95% confidence intervals calculated from PROC LIFETEST output using the method of [[Brookmeyer and Crowley 1982](#)]. Kaplan-Meier estimates of the survivor function with 95% confidence intervals at specific time points will be summarized. The standard error of the Kaplan-Meier estimate will be calculated using Greenwood’s formula [[Collett 1994](#)].

Difference in responder rates stratified by part using Mantel-Hanszel estimate

For PCR corrected and uncorrected ACPR rates, the treatment differences versus control will be evaluated using a Mantel-Haenszel estimate of the treatment difference in responder rates stratified by Part using PROC FREQ with RISKDIFF(COMMON) option in the TABLES statement).

Difference in responder rates using the Wilson uncorrected method

For PCR corrected and uncorrected ACPR rates, the treatment differences versus control will be evaluated using a Wilson uncorrected method using PROC FREQ with RISKDIFF (CL=WILSON) option in the TABLES statement.

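### Kaplan-Meier mean clearance times have no end point common to the arms, so they are not comparable when an arm's longest time is censored

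*Protocol*

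**What the plan says.** For parasite clearance time (PCT) and fever clearance time (FCT), the Protocol summary says that "descriptive statistics (mean, standard error, median, quartiles) for each treatment group will be presented using the Kaplan-Meier method". Protocol 9.5.1.3 asks for the same mean and standard error along with the median and quartiles: "Descriptive statistics (mean, standard error, median, quartiles) will be presented using the Kaplan-Meier method". SAP 2.7.2.3 repeats this.

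The censoring rules are:
- Parasites: "Patients without parasite clearance for whatever reason will be censored at the time of last parasite assessment" (SAP 2.7.2.3; Protocol 9.5.1.3 has the same rule).
- Fever: "Patients without fever clearance for whatever reason will be censored at the time of last temperature assessment" (Protocol 9.5.1.3, repeated in the SAP).
- Added in SAP 2.7.2.3: "Patients who received any antimalarial medication (including rescue medication) before (parasite or fever) clearance will be censored at the first use of antimalarial medication".

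SAP 5.6.3 names the estimator, the product-limit "method as implemented in PROC LIFETEST with METHOD=KM option", and gives no upper time limit for a mean. SAP 2.1.1 has a rule for the tail of Kaplan-Meier plots: for times beyond the last planned assessment, "the time to event will be reset to planned last day regardless of censoring". Patients who never clear are foreseen, because the separate Kaplan-Meier analysis of ACPR says "If a patient parasite is not cleared at all, Day 7 is considered as the event time" (SAP 2.5.4.1). That rule is not applied to PCT or FCT.

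**The concern.** A Kaplan-Meier mean is the area under the curve. When the longest time in an arm is censored, the curve stays above zero and the area has to stop somewhere. With no stated limit, each arm's own data set the stopping point, so the means and standard errors of two arms describe different time spans. A patient who never clears can then add less to the mean than one who clears late, which favours the arm with fewer clearances. The tail rule in SAP 2.1.1 does not cure this. It only pulls times back to the last planned day, leaves uncleared patients censored, and sets no limit for the mean.

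PCT and FCT are secondary endpoints and are among the results reviewed at the end of Part A (SAP 2.15). A reader who compares arms by the mean could be misled there.

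**Working it through.** **Inputs.** The plan gives no figure for mean PCT or FCT, so there is none to reproduce. Arm size comes from Protocol 9.8: 42/(1 − 0.16) = 50 per KAF156/LUM-SDF arm, 21/(1 − 0.16) = 25 for Coartem, and 6 × 50 + 25 = 325, as stated. The clearance times below are assumed, placed on scheduled assessment times (12, 24, 36, 48, 72, 96, 168 h).

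**Formula.** Mean = area under S(t) from 0 to the cut. If the curve is at level S after the last common clearance at time t, one further clearance at t' moves the cut and adds S × (t' − t).

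**Example A, three slow patients in 50.** In both arms 47 patients clear: 3 at 12 h, 12 at 24 h, 15 at 36 h, 12 at 48 h, 5 at 72 h. Their times sum to 36 + 288 + 540 + 576 + 360 = 1800 h. The area to 72 h is (1800 + 3 × 72)/50 = 40.32 h, and S after 72 h is 3/50 = 0.06. In arm X nobody else clears. In arm Y one of the three clears at 168 h and the other two are censored at 168 h or later.

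**Example B, one slow patient in 50.** As above but with 7 clearing at 72 h, so 49 clear and their times sum to 1944 h. In arm X the 50th patient never clears. In arm Y that patient clears at 168 h.

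**Cut at each arm's last clearance (assumed convention).**

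| | Arm X | Arm Y | Y − X |
|---|---|---|---|
| A | 40.32 h | 40.32 + 0.06 × 96 = 46.08 h | 5.76 h |
| B | (1944 + 72)/50 = 40.32 h | (1944 + 168)/50 = 42.24 h | 1.92 h |

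The arm that clears one more patient has the longer mean in both. In an arm of 25, the shift in B would be (1/25) × 96 = 3.84 h.

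**Cut at each arm's last observation (the other convention).**

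| | Arm X | Arm Y |
|---|---|---|
| A, uncleared censored at 168 h | 40.32 + 0.06 × 96 = 46.08 h | 46.08 h |
| A, uncleared censored at 1008 h | 40.32 + 0.06 × 936 = 96.48 h | 46.08 + 0.04 × 840 = 79.68 h |
| B, uncleared censored at 1008 h | 40.32 + 0.02 × 936 = 59.04 h | 42.24 h |
| B, X censored at rescue at 72 h; Y clears at 96 h | 40.32 h | (1944 + 96)/50 = 40.80 h |

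The first row is a tie and the next two are in the right order. The last row still reverses, by 0.48 h, because the SAP's rescue rule ends arm X's curve early.

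**Common limit.** At 72 h every arm above gives 40.32 h, so there is no reversal but also no separation. At 168 h, example B with X followed to 168 h or later gives 42.24 h, against 40.80 h if Y's patient clears at 96 h: the right order. If Y's patient clears exactly at 168 h, the two tie.

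**Other planned summaries.** In both examples S is 0.70 at 24 h, 0.40 at 36 h and 0.16 at 48 h. The lower quartile, median and upper quartile are therefore 24, 36 and 48 h in both arms.

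**The case against.** The strongest reply is that the documents never say where the mean is cut. That is right: stopping at the last clearance is an assumption about the named procedure, and under the other convention the 168 h examples do not reverse. What survives is that either convention leaves the end point to each arm's own data, and the rescue-censored case reverses under both.

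A reader might take the distortion to be larger. If the extra patient in example A cleared at 336 h, the mean would be 40.32 + 0.06 × 264 = 56.16 h, a gap of 15.84 h. The documents do not support that case as typical. Such a patient would ordinarily still have parasites on Day 8, which meets a late-failure definition that warrants rescue (Protocol 5.6.6), and SAP 2.7.2.3 then censors at first antimalarial use. A first clearance seen at 168 h is compatible with the definitions: an afebrile patient below 25% of the Day 1 count on Day 4, and still afebrile on Day 5, has met no failure criterion by count or temperature, and late parasitological failure starts at Day 8.

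A reader might also infer that Part B regimens would be chosen in the wrong order. That is not supported either. Protocol Table 3-2 rests selection on the exact interval for Day 29 PCR-corrected ACPR plus safety. Section 3.3 brings in secondary efficacy parameters only if needed, and nothing ranks cohorts by a mean clearance time. The planned comparison with control is the log-rank test.

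Finally, three uncleared patients in 50 is an assumption, and no fever example was calculated. For FCT only the mechanism is claimed.

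**Conclusion.** The point holds as a minor correction. The plan promises a mean and standard error that are not comparable between arms whenever an arm's longest time is censored, and no passage sets a common limit. On the last-clearance assumption and the illustrative times, the arm with one more clearance looks slower by about 2 h with one slow patient in 50 and by about 6 h with three. On the last-observation convention those examples tie or fall in the right order, and a reversal of about 0.5 h can occur after early rescue censoring. If everyone clears, the mean is complete and the point disappears. Medians and quartiles (where reached), the curves and the log-rank test do not have this fault. No formal decision depends on the mean, although PCT and FCT are reviewed at the end of Part A.

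**What to change.** In the Protocol summary, Protocol 9.5.1.3 and SAP 2.7.2.3, replace the mean and standard error with the restricted mean and its standard error to one pre-specified time common to all arms, or drop the mean. The time must be no later than the shortest of the arms' longest follow-up times; an arm whose curve has already reached zero does not limit it. Either 72 h or a later common time such as 168 h would do, the later one only if follow-up, after rescue censoring, supports it. The choice is a trade-off: 72 h is easier to support but cannot separate arms that differ only afterwards. Keep the median, quartiles, curves and log-rank test, and add the proportion cleared by the chosen time.

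The cost is one sentence in each place and one program option. The downside is that clearances after the chosen time are described only by the curve and the proportion cleared.

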## 1 Introduction

### 1.1 Background

Malaria is one of the most important infectious diseases which threatens about 3.2 billion people, almost half of the world's population. Despite increasing international efforts for malaria control, in 2015, there were 214 million cases worldwide of malaria and 438 000 deaths according to the latest World Health Organization estimates ([WHO 2015](#)). Sub-Saharan Africa carries a disproportionately high share of the global malaria burden. In 2015, the region was home to 88% of malaria cases and 90% of malaria deaths. Also, in areas with high transmission of malaria, children under 5 are particularly susceptible to infection, illness and death; more than two thirds (70%) of all malaria deaths occur in this age group (306 000 estimates deaths in 2015; see [WHO 2015](#)).

Malaria is caused by *Plasmodium* parasites. There are five parasite species that cause malaria in humans, and two of these species – *P. falciparum* and *P. vivax* – pose the greatest threat. *P. falciparum* is the most prevalent malaria parasite on the African continent. It is responsible for most malaria-related deaths globally. *P. vivax* is the dominant malaria parasite in most countries outside of sub-Saharan Africa ([WHO 2015](#)).

Standard antimalarial drugs such as chloroquine (CQ), pyrimethamine (PYR), sulfadoxine (SFDX) and mefloquine (MEF) have become largely ineffective in many malaria endemic regions. The only exceptions are the artemisinin-based combination therapies (ACTs) such as Novartis' Coartem®/Riamet® and Eurartesim®, current standard-of-care for *P. falciparum* malaria. Unfortunately, some recent reports ([Ashley et al 2014](#); [Menard et al 2016](#)) suggest that decades of continuous use of artemisinin and bisquinoline derivatives as monotherapies may have fostered the emergence of drug resistance in *Plasmodium* species in Southeast Asia. Reduced *in vitro* susceptibility of *P. falciparum* to artemisinin in this region has been documented ([Dondorp 2009](#)). Recent studies showed that artemisinin resistance extends over more of Southeast Asia than had previously been known, and is now present close to the border with India ([Menard et al 2016](#)). If widespread artemisinin drug resistance was to occur, malaria pharmacotherapy would be severely impaired. This finding signifies that spread of resistance is inevitable, thus there is urgent need for new antimalarials with new mechanism of actions ([Tun et al 2015](#)).

In addition, current *falciparum* malaria treatments require at least a 3-day dosing regimen which may contribute to therapeutic non-compliance in some patients. Indeed, patients often have resolution of clinical symptoms within 1 to 2 days and may neglect taking final doses. This may contribute to the development of drug resistance.

There is therefore a strong medical need for new chemical entities with a new mode of action as additional treatment options for this very common disease with substantial morbidity and mortality. Simplifying regimens by developing treatments that can be used in a once daily dose for less than 3-day administration can improve treatment success and reduce probability of developing resistance via improved adherence and thus accelerate malaria eradication.

The purpose of this study is to determine the effective and tolerable dose of KAF156, a new antimalarial molecule that can be administered in combination with a Solid Dispersion Formulation of lumefantrine (LUM-SDF) for the shortest treatment duration possible.

KAF156 is the first drug from a different and novel class of drugs called imidazolepiperazines and was developed by the Novartis Institute for Tropical Diseases (NITD) following a high through-put screening (HTS) of the Novartis compound library by the Genomics Institute of the Novartis Research Foundation (GNF). KAF156 is structurally distinct from currently marketed antimalarial drugs and other experimental antimalarial compound classes currently in development. The mechanism of action of KAF156 is still being characterized, but may be related to a previously uncharacterized gene (*Plasmodium falciparum* cyclic amine resistance locus, Pfcarl). KAF156 kills/inhibits the erythrocytic replication life cycle stages (blood stages) of the two main causative agents of human malaria, *P. falciparum* and *P. vivax*, both at low nanomolar EC50s (*in vitro*). In addition, KAF156 has shown activity in liver stage models of *Plasmodium* infection, conferring causal prophylactic protection in animal infection models. Limited evidence of gametocytocidal activity may confer transmission blocking activity. KAF156 has not demonstrated activity against liver hypnozoites and therefore has a low probability to be used for a radical cure for *P. vivax*. Also, KAF156 is equally potent against drug-sensitive and a broad panel of drug resistant malaria strains (Kuhlen et al 2014).

KAF156, when combined in a fixed-dose formulation with an anti-malarial partner drug, could offer a much needed new treatment for malaria, including in areas where resistance to ACTs is emerging. A fixed-dose formulation with a single-dose regimen to ensure patient adherence to the full treatment would be an ideal option. However, the development of such single-dose regimens are more challenging in terms of maintaining adequate blood levels during 6-7 days (3 parasite replication cycles). Considering the impending risk of resistance to existing antimalarials and higher risk of therapeutic failure with a single- or two day regimen, a three day regimen will also be evaluated with the simultaneous exploration of one and two day treatment regimen in order to reduce the overall development risk and address the critical unmet medical need due to emerging resistance to standard therapy.

Lumefantrine-Solid Dispersion Formulation (SDF) will be used as partner drug in this study. In contrast to the conventional lumefantrine formulation, lumefantrine-SDF has an improved absorption profile and less food effect, leading to exposure which allows for a once-daily regimen. LUM-SDF is expected to have a similar safety profile to conventional LUM used as partner drug in Coartem®.

KAF156 and lumefantrine will be administered as combination for the first time in this study. Based on their metabolism, no clinically relevant interaction is expected between KAF156 and lumefantrine. However, in a recent preclinical *in vivo* study in dogs KAF156 (10 mg/kg) and LUM-SDF (15 mg/kg) were administered in combination and preliminary data suggest that exposure of both KAF156 and lumefantrine increased in presence of each other. There was around 2-3 fold increase in KAF156 exposure and around 1.5 fold increase in lumefantrine exposure.

A slightly increased lumefantrine exposure is not considered of clinical significance as it was anticipated, based on potential metabolic interaction. KAF156 is a weak CYP3A4 inhibitor based on an interaction study with piperazine and can potentially increase lumefantrine exposure slightly. However, in clinical interaction studies of lumefantrine with strong CYP3A4 inhibitors such as ketoconazole (Lefevre et al 2002) and lopinavir/ritonavir-based antiretroviral (Kredo et al 2016) despite up to 5 fold increase in lumefantrine exposure it was concluded that

this interaction did not result in lumefantrine exposures above seen in patients following a standard dose of Coartem (Lefevre et al 2001).

On the other hand, increased KAF156 exposure was unanticipated and there is no sufficient data to cover for exposure for the highest doses of KAF156 in this study, should KAF156 exposure increase by 2 fold. The dog data suggest that increased KAF156 exposure potentially occurs because of interaction of LUM-SDF with KAF156 at absorption-level which in turn suggest that interaction may not lead to more than 2 fold increase in KAF156 exposure in human given its estimated bioavailability of at least 50% in humans. There is no experience of KAF156 exposure beyond that of 1200 mg single dose or 600 mg daily for 3 days. Given the above situation, the first part of the study will explore the PK and safety of KAF156 given in combination with LUM-SDF to understand the impact of LUM-SDF on KAF156 exposure as victim drug. In the unlikely scenario of an increase in KAF156 exposure beyond the acceptable limit, doses in Part A of the study may be adjusted (as described in Section 3.3).

